9.2.4 Duration of Response

Duration of Response (DOR) for patients in Group A is a secondary endpoints for this study; DOR for Group B is an exploratory endpoint. DOR is defined as the time that measurement criteria are met for CR or PR (whichever is first recorded) until the first date that recurrent or progressive disease is objectively documented or to death due to any cause in the absence of documented PD.

The Kaplan-Meier method will be used for the subgroup of patients with a confirmed objective response in order to obtain the estimate of median DOR. Censoring for the DOR

endpoint will be assigned on the date of the last tumor assessment if no assessment of tumor progression is recorded and the patient does not die and prior to the start of subsequent anti-cancer therapy. Descriptive statistics will be provided for the DOR in responding patients (i.e., median duration of response and 95% CIs) by cohort, including the associated Kaplan-Meier curves.

9.2.5 Clinical Benefit Rate

Clinical Benefit Rate (CBR) in Group A is a secondary endpoints for this study, while CBR in Group B is an exploratory endpoint. CBR is defined as the percent of patients documented to have a confirmed Complete Response (CR), confirmed Partial Response (PR), or Stable Disease (SD) documented on at least 1 on-study assessment and including at least 5 weeks on study. An approach similar to that described for analysis of ORR (Section 9.2.1) will be used to assess CBR.

9.2.6 Intracranial Objective Response Rate

Intracranial Objective Response Rate (iORR) in patients with baseline CNS metastases is an exploratory endpoint of this study. iORR will be determined by the proportion of patients with a brain metastasis response in clinically evaluable lesions using RANO-brain metastasis criteria. RANO-brain metastases criteria is summarized briefly in Appendix 4.

9.2.7 Intracranial Duration of Response

Intracranial duration of response in patients with baseline CNS metastases is an exploratory endpoint of this study. iDOR is defined as the time from first complete intracranial response or partial intracranial response (whichever is documented first) to date of intracranial disease progression (not considering extracranial disease progression). An approach similar to that described above for DOR will be used to assess iDOR (Section 9.2.4).

9.2.8 Intracranial Progression Free Survival

Intracranial Progression Free Survival (iPFS) in all patients regardless of the presence of baseline CNS metastases is an exploratory endpoint of this study. iPFS is defined as the time from first dose to the date of first intracranial progressive disease (as per RANO-brain metastasis criteria). An approach similar to that described for the analysis of PFS (Section 9.2.3) will be used.

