¹⁰ Full physical exam should be performed at screening, C1D1 and End of Treatment visit. At other visits, symptom directed exam is permissible

¹¹ Window for echocardiogram and radiologic assessments is -7 days; screening imaging and ECHO should be completed no more than 28 days prior to starting trial drug; first on study imaging to occur 6 weeks (+/- 7 days) after C1D1

¹² Following mandatory ECHO with C3, further ECHOs only need to be performed if there are clinical concerns for cardiac disease (eg signs or symptoms concerning for heart failure, pericarditis, tamponade, pulmonary hypertension)

¹³ Pregnancy Test: If the patient is a woman of childbearing potential, negative serum or urine pregnancy test performed by the local laboratory at screening will be required. The informed consent process must include discussion of the risks associated with pregnancy and adequate contraception methods. Additional pregnancy testing may be necessary if required by local practices or regulations, or if potential pregnancy is suspected.

¹⁴ MRI brain (or CT head with contrast if MRI is contraindicated) should be performed on schedule with other radiologic disease evaluations if there is known CNS disease. If no known CNS metastases, MRI brain/CT head with contrast should be performed as clinically indicated

¹⁵ If study treatment is discontinued prior to disease progression, disease assessments should continue as per study protocol until the time of disease progression or start of new therapy

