7.1 Efficacy Assessments

7.1.1 Radiographic Disease Assessment

All patients enrolled in the study are to undergo disease evaluations as outlined in the Study Calendars (Section 6.1). If symptoms develop or clinical deterioration occurs, patients may be imaged prior to the pre-specified time points for imaging. Patients discontinuing treatment prior to objective disease progression will be followed by radiographic evaluation until disease progression is documented or until the start of subsequent anti-cancer therapy, whichever is sooner.

Screening/baseline tumor assessments should include CT (with contrast, unless contraindicated) of the chest and abdomen (plus pelvis if indicated) and MRI of the brain

with and without gadolinium (preferred) or head CT with contrast if MRI is contraindicated. The allowable windows for screening/baseline assessments is 28 days prior to randomization.

Disease assessments performed on-study will include CT of the chest/abdomen (plus pelvis if indicated) and assessment of all known and suspected sites of disease. MRI brain should be performed on schedule with other radiologic disease evaluations if there is known CNS disease. If no known CNS metastases, MRI brain should be performed as clinically indicated. Assessments will be performed as per study calendars: every 6 weeks (starting from C1D1) for 3 months, every 9 weeks for 9 months and every 12 weeks thereafter. The allowable windows for on-study assessments is +/- 7 days. Assessments will be performed until objective disease progression is documented by the Investigator, or subsequent anti-cancer therapy is begun.

The Investigator's assessment of disease response and progression per RECIST 1.1 (for extracranial disease) and RANO-BM criteria (for intracranial disease) will be the basis for patient management and statistical analyses of radiology-based study endpoints. RECIST v1.1 and RANO-BM criteria are summarized in Appendices 3 and 4.

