7.1.3 CNS Disease Assessment

Intracranial Objective Response Rate (iORR), Intracranial Duration of Response (iDOR) and Intracranial Progression Free Survival (iPFS) are all exploratory endpoints of this study. MRI or CT head with contrast (as above) will be assessed at baseline for evidence of CNS disease and ongoing CNS imaging evaluation will be performed thereafter at intervals as per the Study Calendars (Section 6.1). CNS tumor response assessment will be performed

according to RANO-brain-metastasis criteria, summarized in Appendix 4. Clinical status and steroid requirement will be assessed and documented at each study visit as per Study Calendars (Section 6.1).

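### iPFS covers all patients, but without known CNS disease no brain scan is scheduled after screening, so the pooled curve tends to overstate intracranial control; handling of death is not stated

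*Combined protocol and SAP*

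**What the plan says.** **Population.** "Intracranial Progression Free Survival (iPFS) in all patients regardless of the presence of baseline CNS metastases is an exploratory endpoint of this study" (9.2.8). The synopsis, 3.3 and 4.4.3 also refer to all patients.

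**Event and analysis.** 9.2.8 names one event: "iPFS is defined as the time from first dose to the date of first intracranial progressive disease (as per RANO-brain metastasis criteria". It then says "An approach similar to that described for the analysis of PFS (Section 9.2.3) will be used". Section 9.2.3 counts progression or death for PFS and censors event-free patients at their most recent tumor assessment. Section 9.5 repeats that censoring rule for all time-to-event analyses. Neither section requires the assessment to be a brain image.

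**Brain imaging.** Everyone has a brain MRI, or a head CT if MRI is contraindicated, at screening. On study, patients with known CNS disease are scanned on the body-imaging schedule. For the others, "If no known CNS metastases, MRI brain should be performed as clinically indicated" (7.1.1), and footnote 14 of both calendars agrees: "If no known CNS metastases, MRI brain/CT head with contrast should be performed as clinically indicated". Section 7.1.3 states that "ongoing CNS imaging evaluation will be performed thereafter at intervals as per the Study Calendars", but the calendars set no interval for these patients.

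**New lesions.** Appendix 4 exempts new brain lesions during immunotherapy-based treatment from its list of progression events. It then says that new lesions by themselves might not amount to progression in that setting.

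**The concern.** A progression-free curve relies on looking for progression in everyone at known times. Here one part of the population is looked at on a schedule and the other only when something prompts a scan. In the second part, a clear chest and abdomen CT extends the time counted as free of brain progression although the brain was not imaged. Undetected or late-detected progressions push the curve up, and pooling hides which part of it rests on scans.

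The event is also incompletely specified. PFS (9.2.3) and DOR (9.2.4) name death; iPFS (9.2.8) and iDOR (9.2.7) do not. For a patient with no CNS lesion at baseline, a new lesion is the only possible first intracranial event, and Appendix 4 leaves open whether it counts.

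Section 3.3 hypothesises improved iPFS, so a curve is likely to be reported. No test or decision rule depends on it.

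**Working it through.** The documents give no iPFS event count, rate or precision, so there is no stated figure to reproduce. All rates below are assumptions.

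**1. Scheduled scans over two years** (7.1.1). Every 6 weeks for 3 months: weeks 6, 12. Every 9 weeks for 9 months: weeks 21, 30, 39, 48. Every 12 weeks thereafter: weeks 60, 72, 84, 96. That is 2 + 4 + 4 = 10 body CTs. Scheduled brain scans after screening without known CNS disease: 0.

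**2. Patients without known CNS disease, half of brain progressions undetected, deaths not events.** With a constant brain-progression rate h per month, true 12-month freedom is exp(−12h). If a fraction d is detected promptly, the body-CT-censored curve shows about exp(−12hd). With d = 0.5:
- h = 0.005: exp(−0.03) − exp(−0.06) = 0.970 − 0.942 = 0.029
- h = 0.01: exp(−0.06) − exp(−0.12) = 0.942 − 0.887 = 0.055

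A simulation with the protocol's visit times gave +0.027 to +0.029 and +0.053 to +0.055, hence about 3 to 6 points.

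**3. All-patient curve, wider assumptions.** The plan was compared with scheduled brain scans for everyone (40,000 simulated patients per scenario). Inputs: 12-month intracranial progression 10–30%; baseline CNS disease in 15–30%; median extracranial PFS 8 months; median OS 20 months. Shift in 12-month iPFS, in percentage points:

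| Clinical detection | Mean delay | Death not an event | Death an event |
|---|---|---|---|
| 100% | 1 month | −0.5 to −0.2 | −0.1 to +0.2 |
| 100% | 3 months | +0.8 to +3.5 | +0.7 to +3.0 |
| 50% | 3 months | +3.8 to +13.7 | +2.5 to +9.0 |

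**4. Handling of death.** In the same runs, counting death as an event lowers the 12-month estimate by about 24 to 33 points (for example 0.908 to 0.605, and 0.716 to 0.475). That is larger than any shift in step 3.

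**5. Would censoring everyone at the last brain image repair it?** Suppose 25 patients have no known CNS disease, 3 have symptomatic brain progression at months 4, 8 and 11, and 22 have only the screening scan. With body-CT censoring beyond month 12, 12-month freedom is 22/25 = 88%. With brain-image censoring the 22 leave at baseline, the risk set is the 3 patients with events, and the curve runs 2/3, 1/3, 0. The second rule selects on having had a reason to be scanned, so it is no remedy here.

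**The case against.** **A reader might infer that the plan permits either 88% or 0% from the same data, and that the curve therefore cannot be interpreted.** The documents do not support that. The censoring rule in 9.2.3 and 9.5 has no restriction by modality, and 7.1.1 describes on-study assessment as "CT of the chest/abdomen (plus pelvis if indicated) and assessment of all known and suspected sites of disease". The natural reading is censoring at the last scheduled assessment, usually a body CT. The 0% also needs every event-free patient to have no negative for-cause scan. With such scans in an assumed 2% of patients per month, simulated 12-month values under brain-image censoring are 47–86% (deaths not counted). With deaths counted, the two censoring rules differ by 5 to 14 points. The curve can be read as time to clinically detected progression, if it is labelled so.

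**Size against noise.** For 88% in 25 patients the 95% half-width is 1.96 × √(0.88 × 0.12/25) ≈ 13 points; for 90% in 70 it is about 7. A 3 to 6 point bias is smaller than either. This stands, and it limits severity.

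**Death.** The references from 9.2.8 to 9.2.3 and from 9.2.7 to 9.2.4 probably import death. It would be wrong to say that the plan excludes it. What remains is that it is not stated, and step 4 shows that it matters.

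**When scans stop.** One might infer from 7.1.1 that all imaging ends at first progression, leaving many deaths long after the last brain scan. Section 6.8 calls for a repeat assessment after progression and allows treatment to continue, so this cannot be assumed.

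**New lesions.** Appendix 4 is an abbreviated summary and its two sentences can be read together. They still do not give the endpoint rule.

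**Conclusion.** The point holds as a minor one. The all-patient iPFS combines scheduled with symptom-triggered detection and credits time without brain imaging as progression-free. The likely direction is overstatement: about 3 to 6 points at 12 months in patients without known CNS disease if half of brain progressions are missed, and roughly 0 to 14 points for the pooled curve over wider assumptions. The bias is close to zero if every progression is detected clinically within about a month. These sizes rest entirely on assumed rates. The gaps in the text do not: no brain-imaging interval without known CNS disease, no iPFS-specific censoring rule, and no explicit statement on death or new lesions. The endpoint is exploratory and the ORR decision is unaffected.

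**What to change.** Change wording and analysis only; no extra scans are needed.

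- **9.2.8, baseline CNS disease:** report Kaplan-Meier iPFS with the event defined as intracranial progression or death from any cause, consistent with 9.2.3. Censor event-free patients at the last brain MRI or CT.
- **9.2.8, no baseline CNS disease:** report cumulative incidence of intracranial progression with death as a competing event, and label it as clinically detected. State where follow-up ends. The last study visit is a workable choice, since "Clinical status and steroid requirement will be assessed and documented at each study visit" (7.1.3).
- **9.2.7:** state that death is handled as in DOR.
- **Endpoint rule for Appendix 4:** state whether a new brain lesion on study treatment counts as intracranial progression.
- **Optional:** a sensitivity analysis for deaths long after the last brain scan.

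Cost: two summaries replace one curve. The Kaplan-Meier group may be small, and the documents give no expected number with baseline CNS disease. The references to all patients in the synopsis, 3.3 and 4.4.3 must be aligned.

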9.3 Safety Analysis

Evaluation of the safety and toxicity profile of the combination of sitravatinib and pembrolizumab in the first-line treatment of patients with non-squamous metastatic NSCLC is a secondary objective in this study. Secondary endpoint is adverse events as per CTCAE v.5. The Safety population is defined as all patients who received any dose of study treatment (i.e., sitravatinib and/or pembrolizumab) and will be used for all safety analyses.

9.4 Correlative Analyses Plan

- Wilcoxon's rank-sum test will be used to compare the % of T_{effector}, % of myeloid activation, % of CD 8⁺ T cells and % of FOXP3⁺ T cells between AXL hi versus lo ($\geq 50\%$ and $<50\%$, respectively) and MERTK high versus low groups.
- Comparisons between pre- and post-treatment will be evaluated by Wilcoxon signed rank test.
- To compare differences (% change) between sitravatinib + pembrolizumab versus pembrolizumab alone, Wilcoxon's rank-sum test will be used.
- To compare differences in sitravatinib + pembrolizumab treatment across cohorts with distinct PD-L1 status Wilcoxon's rank-sum test will be used.
- Baseline or changes in immune cell populations will be compared between responders and non-responders using Wilcoxon rank sum test.
- Single-cell RNA sequencing and bulk RNA sequencing are exploratory pilot assessments.

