3.3 Exploratory Objectives and Hypotheses

(1) Objective: To evaluate ORR, OS, PFS, DOR, CBR in patients with treatment naïve advanced PD-L1 positive NSCLC who receive a 3 week pembrolizumab run-in followed by treatment with pembrolizumab/sitravatinib combination therapy.

Hypothesis: The combination of pembrolizumab/sitravatinib with a pembrolizumab run-in will improve clinical outcomes in patients with treatment naïve, metastatic PD-L1 positive non-squamous NSCLC.

(2) Objective: To evaluate CNS activity of the combination of sitravatinib and pembrolizumab by measuring intracranial ORR (iORR) and intracranial duration of response (iDOR) in patients with baseline CNS disease in the main study population, and intracranial progression-free survival (iPFS) in all patients.

Hypothesis: The combination of pembrolizumab/sitravatinib will result in improved iORR, iDOR, and iPFS.

(3) Objective: To study correlates of the adaptive and innate immune responses induced by sitravatinib and pembrolizumab treatment in both tumor tissue and peripheral blood.

Hypothesis: The combination of pembrolizumab with sitravatinib will increase the percentage of CD68+HLA-DR+CD163- myeloid cells as well as the percentage of effector CD3+GranzymeB+Ki67+ T cells in the tumor microenvironment (TME). The percentage change upon treatment with pembrolizumab + sitravatinib will be greater in patients receiving the combination than in patients treated with pembrolizumab alone.

The above-mentioned changes will be observed in samples with >50% AXL⁺ and MERTK⁺ CD68⁺ myeloid cells before treatment and AXL and MERTK expression will inversely correlate with percentage of effector CD8⁺ T cells and positively with FOXP3⁺ T regulatory cells. Upon treatment, the percentage of effector CD8⁺ T cells are expected to increase with a concomitant reduction in FOXP3⁺ T regulatory cells.

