4.4.3 Exploratory Endpoints

(1) ORR, PFS, OS, DOR in the pembrolizumab run-in population. These results will not be included in the analysis of the main study population, but will be used to generate a preliminary assessment of benefit with this strategy.

(2) Intracranial Objective Response (iORR) and intracranial Duration of Response (iDOR) in patients with baseline CNS disease (Sections 9.2.6 and 9.2.7).

(3) Intracranial Progression Free Survival (iPFS) in all patients (Section 9.2.8).

(4) Correlative Endpoints:

- a. Percentage of activated myeloid cells, effector T cells, and AXL+/MERTK+ macrophages in the TME as assessed by multiplex qualitative immunofluorescence in pre- and post-treatment tissue samples in both the main study population and pembrolizumab run-in population.
- b. Clinical response as correlated to immune populations present in baseline samples and immune cell population changes induced by therapy
- c. Immune cell population changes in the TME as defined by changes in population heterogeneity detected by single cell RNA in pre- and post-treatment tissue samples in both the main study population and pembrolizumab run-in population
- d. Gene expression changes in peripheral blood mononuclear cells in pre- and post-treatment tissue samples in both the main study population and pembrolizumab run-in population.
- e. Percentage of CD8⁺ T cells and FOXP3⁺ T regulatory cells in pre- and post-treatment tissue samples in both the main study population and pembrolizumab run-in population.
- f. The percentage of CD8⁺ T cells and FOXP3⁺ T regulatory cells correlated with the percentage of activated myeloid cells and AXL+/MERTK+ macrophages in the TME in pre- and post-treatment tissue samples in both the main study population and pembrolizumab run-in population.

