11.3.2 Multiplex Quantitative Immunofluorescence

Analysis of the tumor microenvironment will be done using multiplexed quantitative immunofluorescence (QIF) to spatially map the MERTK pathway (MERTK, Axl and Tyro3), major T-cell subsets (CD4, CD8 and FOXP3) and tumor-associated macrophages (CD11b, CD68, HLA-DR or CD163). QIF will be performed on tumor tissue from baseline and 3 week on-treatment tissue samples from 30 patients as outlined above. A minimum of 4 panels are planned as listed below:

- Panel 1: Dapi-CK-CD3-GranzymeB-Ki67
- Panel 2: Dapi-CD68-Cd11b-CD163-HLA-DR A
- Panel 3: Dapi-CK-CD68-MERTK-AXL
- Panel 4: Dapi-CK-CD8-CD4-FOXP3

Percentage of activated myeloid cells, effector T cells and AXL+ and MERTK+ macrophages in the TME will be measured and compared in pre- and post-treatment samples for patients treated with sitravatinib/pembrolizumab combination versus pembrolizumab alone. The expression of AXL and/or MERTK in CD68⁺ cells will be correlated with the percentage of CD8⁺ T cells, FOXP3⁺ T regulatory cells, effector T cells and activated myeloid cells across multiple stained sections.

Additional panels may be added. For full details please see Laboratory Manual.

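### The AXL/MERTK endpoint is described as a correlation, but section 9.4 names no correlation method and gives only a high/low split, which is likely to lose power with 30 patients

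*Combined protocol and SAP*

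**What the plan says.** Section 3.3, under the third exploratory objective, makes two separate statements.

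- A threshold statement: "The above-mentioned changes will be observed in samples with >50% AXL"-positive and MERTK-positive CD68+ myeloid cells before treatment. It says in which samples the treatment changes are expected.
- A correlation statement: "AXL and MERTK expression will inversely correlate with percentage of effector" CD8+ T cells, and correlate positively with FOXP3+ cells.

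Section 4.4.3, item (4)f, makes the correlation an exploratory endpoint: CD8+ and FOXP3+ "T regulatory cells correlated with the percentage of activated myeloid cells and AXL+/MERTK+ macrophages in the TME". It covers pre- and post-treatment tissue in both Group A and Group B. Section 11.3.2 repeats the intention with a longer list. "The expression of AXL and/or MERTK in CD68"+ cells is to be correlated with CD8+, FOXP3+, effector T-cell and activated-myeloid percentages. It names no coefficient or test.

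In 9.4 the only analysis that relates AXL or MERTK to other cell percentages is a group comparison: "Wilcoxon's rank-sum test will be used to compare the % of" effector T cells, activated myeloid cells, CD8+ cells and FOXP3+ "T cells between AXL hi versus lo" groups, and likewise for MERTK. AXL is cut at 50% or more versus less than 50%. MERTK is called high or low with no level attached. The general plan in 9.1.2 lists t-tests, Wilcoxon tests, chi-square and Fisher tests, and no correlation or regression method. No significance level, power or effect size is given for the correlatives.

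**The concern.** An endpoint defined as a correlation between two continuous percentages has no matching method in the section that sets the methods. The analysis given in its place reduces one of the two variables to high or low. That discards information, and the loss grows if the fixed cut leaves few patients on one side. The documents do not say what share of patients is expected above 50%.

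The split is also loosely specified:

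- The MERTK level is not stated, so it could be chosen after the data are seen.
- Section 3.3 uses more than 50% and names AXL and MERTK together. Section 9.4 uses 50% or more and takes each marker separately.
- Section 9.4 names no time point, although each patient supplies two biopsies.
- Section 11.3.2 speaks of correlating over several stained sections, which leaves the unit of analysis open.

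At stake is whether a modest sample, obtained through required biopsies, can show the association that the protocol sets out to study.

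**Working it through.** **Sample size.** Section 11.3.1 processes paired tissue for 15 patients per cohort: 5 from Group B and 10 from Group A. Then 2 × (5 + 10) = 30, which reproduces the 30 patients in 11.3.2. These are 30 patients with two dependent samples each, so 30 is the unit for a correlation at one time point. Biopsy exemptions under 6.5.1 can lower it.

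**Assumptions not in the documents.** Two-sided 5%; marker and immune percentage bivariate normal (hence monotone) with correlation rho; share of patients above the cut varied over 50%, 30%, 20% and 10%. The simulated shares above the cut were 50, 70, 80 and 90%. By symmetry the results are the same for 30, 20 and 10%.

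**Method.** For each case, 20,000 data sets were simulated. Spearman's coefficient on the continuous marker was tested with t = r·√[(n − 2)/(1 − r²)]. The split was tested with the exact rank-sum test. The simulation standard error is at most √(0.25/20,000) = 0.0035, or about 0.4 percentage points.

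**Power, n = 30**

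| rho | Spearman | 50% high | 30% high | 20% high | 10% high |
|---|---|---|---|---|---|
| 0.3 | 33% | 23% | 21% | 18% | 12% |
| 0.4 | 56% | 39% | 36% | 30% | 19% |
| 0.5 | 77% | 58% | 53% | 45% | 29% |
| 0.6 | 93% | 78% | 72% | 63% | 40% |

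With rho = 0 the rejection rates are 5.0% for Spearman and 4.8%, 4.7%, 4.6% and 3.6% for the split. Spearman's advantage is therefore not bought with excess false positives.

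**Large-sample check.** The efficiency of a split with share s high, relative to the continuous (Pearson) analysis, is φ(c)²/[s(1 − s)], where c is the normal cut-point and φ the normal density.

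- s = 0.5: 0.3989²/0.25 = 0.64
- s = 0.3: 0.58
- s = 0.2: 0.49
- s = 0.1: 0.34

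A median split thus behaves like discarding about 36% of the sample, a 20% split about half, and a 10% split about two thirds.

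**Equivalent sample size at rho 0.5.** A median split gave 74.6% with 42 patients and 81.0% with 48. Interpolating to 76.7% gives 42 + 6 × (76.7 − 74.6)/(81.0 − 74.6) ≈ 44 patients. With 20% high, the split gave 73.6% with 55 and 79.2% with 62, so 55 + 7 × (76.7 − 73.6)/(79.2 − 73.6) ≈ 59. Either compares with 30 for Spearman.

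**If each PD-L1 cohort is analysed alone (n = 15), rho 0.5.** Spearman has 43%; the split has 28%, 25%, 19% and 10%. Section 9.1.2 calls for separate analyses but names Cohorts A and B, which are the labels of the groups, so whether this case applies is uncertain.

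**The case against.** The strongest reply is that the analysis is not absent. Section 11.3.2 states that the markers will be correlated with all four measures, and it refers to a Laboratory Manual that is not among the documents. That stands: a reader might infer that no correlation is planned at all, and the text does not support this. The gap is that 9.4 specifies no method for it.

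A reader might also infer that 50% is an arbitrary cut. It is not. Section 3.3 states a hypothesis at that level, so the split has a purpose of its own, although no rationale is given for the value. Section 3.3 also suggests 50% for MERTK, but 9.4 does not say so.

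Nor can 9.4 be faulted for failing to restrict the endpoint to baseline. Item (4)f covers both time points, and the words on pre-treatment status in 3.3 belong to the threshold statement. The three sections also differ in scope. Only 11.3.2 correlates AXL/MERTK with all four measures. Section 3.3 names effector CD8+ and FOXP3+ cells, and (4)f sets CD8+ and FOXP3+ against activated myeloid cells as well as AXL/MERTK.

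The size of the loss rests on assumptions. Under a step at 50% the split loses little, and at rho 0.3 neither method is well powered. Both points stand, but 3.3 and (4)f describe a correlation, not a step, and Spearman has the higher power at every rho in the table.

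Finally, 11.3.1 makes the comparison of combination with pembrolizumab alone the primary focus of the tissue work. It would be too strong to call this association the trial's test of its mechanism.

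**Conclusion.** The mismatch is real: a stated correlation endpoint, and a methods section whose only matching analysis is a dichotomised comparison with an incomplete cut definition. For 30 patients, a monotone bivariate-normal relation and two-sided 5%, the split costs about 10 to 19 percentage points of power at a median split for rho between 0.3 and 0.6. It costs more if the groups are unequal: at rho 0.5 the loss is 77 − 45 = 32 points with 20% high and 77 − 29 = 48 points with 10% high. The correlation, the shape of the relation, the significance level and the share above 50% are all assumed.

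This is an improvement worth making in an exploratory analysis. It does not bear on the primary endpoint or on the Simon designs.

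**What to change.** In 9.4, add a Spearman correlation and name it as the analysis for the correlation endpoint:

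- Use one value per patient per time point, with baseline and on-treatment samples analysed separately and stratified by PD-L1 cohort. State how this stands with the separate-analysis rule in 9.1.2.
- Correlate the continuous AXL+ and MERTK+ percentages of CD68+ cells with the CD8+, FOXP3+, effector T-cell and activated-myeloid percentages.
- Correlate CD8+ and FOXP3+ with activated myeloid cells, as 4.4.3 (4)f requires.
- Show the on-treatment result by Group A and Group B too, because the groups have received different treatment by that biopsy.

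Keep the 50% rank-sum split for the separate hypothesis in 3.3 about where treatment changes occur. Define the groups from baseline values, with the same cut and the same marker definition as 3.3 for both AXL and MERTK.

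The cost is wording only, since samples and assays are unchanged. The downside is more tests: 2 markers × 4 percentages + 2 = 10 coefficients per time point, or 20 in all. About 20 × 0.05 = 1 would reach nominal 5% by chance if no association existed. Report them as unadjusted and hypothesis-generating, with estimates and confidence intervals.
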